4.2.2.11.1 Safety Analysis Set

The analyses described in the above section 4.2.2.11 will be produced using the SAF for:

- savolitinib (300 mg od, 300 mg bid and 600 mg od, respectively) in combination with osimertinib in patients with EGFRm+, MET amplified/overexpressed (FISH10+ and/or IHC90+), locally advanced or metastatic NSCLC who have progressed following osimertinib
- savolitinib (300 mg bid, 300 mg bid and 600 mg od, respectively) in combination with osimertinib in patients with EGFRm+, MET amplified/overexpressed (FISH5+ and/or IHC50+), locally advanced or metastatic NSCLC who have progressed following osimertinib

4.2.2.12 Exploratory Endpoint – EQ-5D-5L

The five dimensions will be summarised with the number and proportion of patients in each response category over time for each diagnostic population and by savolitinib starting dose. The EQ-5D-5L index score and the EQ-VAS score will be summarised by descriptive statistics over time.

4.2.2.12.1 Safety Analysis Set

The analyses described in the above section 4.2.2.12 will be produced using the SAF for:

- savolitinib (300 mg od, 300 mg bid and 600 mg od, respectively) in combination with osimertinib in patients with EGFRm+, MET amplified/overexpressed (FISH10+ and/or IHC90+), locally advanced or metastatic NSCLC who have progressed following osimertinib
- savolitinib (300 mg bid, 300 mg bid and 600 mg od, respectively) in combination with osimertinib in patients with EGFRm+, MET amplified/overexpressed (FISH5+ and/or IHC50+), locally advanced or metastatic NSCLC who have progressed following osimertinib

4.2.2.13 Exploratory Endpoint – Change in TL Tumour Size and Best Percentage Change in TL tumour size

4.2.2.13.1 Target Population Analysis Set

Percentage change from baseline in target lesion tumour size at Week 12 and over time, will be summarised.

Also, the best percentage change in tumour size from baseline over all tumour assessment time points will be summarised using descriptive statistics (n, mean, standard deviation, median, minimum, maximum).

The number and percentage of patients with new lesions by lesion site (e.g., CNS) will be tabulated. Waterfall plots showing the percentage change at Week 12 and the best percentage change from baseline in sum of the diameters of TLs will be produced.

Spider plots showing the percentage change from baseline in tumour size for each patient over time may be produced. These plots depict each patient's percentage change in TL tumour size as a line over time. Imputation will not be used for spider plots.

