7.1.3 Follow-up of patients post discontinuation of study intervention

As a minimum, telephone contact should be made with the patient 28 days following the discontinuation of both IPs to collect new AEs and follow up on any ongoing AEs and concomitant medications (including any subsequent cancer therapy, if appropriate). Refer to Section 8.3.3 for full details on AE recordings during follow-up.

Patients who have discontinued study intervention prior to RECIST 1.1 defined radiological progression will be followed up with tumour assessments as indicated in the SoA until RECIST 1.1-defined PD or death regardless of whether or not the patient started a subsequent anti-cancer therapy, unless they have withdrawn all consent to study related assessments.

All patients will be followed for survival until the end of the study.

Patients who decline to return to the site for evaluations should be contacted by telephone as indicated in the SoA as an alternative.

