3 DESCRIPTION OF VARIABLES

3.1 General principles

3.1.1 Baseline measurements and change from baseline variables

Baseline for patients allocated/randomised to treatment will be the last assessment of the variable under consideration prior to the intake of the first dose, except for efficacy variables. For efficacy variables, baseline is defined as the last non-missing assessment prior to randomisation (patients enrolled under CSP version 7.0) or last non-missing assessment prior to first dose (patients enrolled prior to CSP version 7.0). For patients who cross over from savolitinib plus placebo to savolitinib plus osimertinib, their data will be cut off for the purposes of any savolitinib plus placebo assessment at the last assessment of the variable under consideration prior to the intake of the first dose of the combination therapy.

If two assessments are equally eligible to assess patient status at baseline (e.g. on the same date prior to first dose with no time recorded to distinguish the assessments), the average should be taken as the baseline value. For non-numeric laboratory tests (i.e. some of the urinalysis parameters) where taking an average is not possible then the best value would be taken as baseline as this is the most conservative. In the scenario where there are two assessments on Day 1, one with time recorded and the other without time recorded, the one with time recorded would be selected as baseline, assuming it could be determined that it occurred prior to first dose. Where safety data are summarised over time, study day will be calculated in relation to date of first treatment. If no value exists before the first dose/administration, then the baseline value will be treated as missing.

Regarding electronic Patient reported outcome [ePRO] questionnaires, the baseline is defined as the non-missing assessment collected at Day 1, as it is assumed it is taken prior to start of the study treatment. If an assessment is missing at Day 1, the prior non-missing assessment will be used as baseline.

In all summaries change from baseline variables will be calculated as the post treatment value minus the

value at baseline. For % change from baseline, calculate:

$$\% \text{ change from baseline} = \frac{(\text{Post baseline value} - \text{Baseline Value})}{\text{Baseline value}} \times 100$$

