If a TL becomes too big to measure this should be indicated in the database and a size ('x') above which it cannot be accurately measured should be recorded. If using a value of x in the calculation of TL response would not give an overall visit response of PD, then this will be flagged and reviewed by the study team. It is expected that a visit response of PD will remain in the vast majority of cases.

TL too small to measure

If a TL becomes too small to measure, then this will be indicated as such on the case report form and a value of 5mm will be entered into the database and used in TL calculations. However, a smaller value may be used if the radiologist has not indicated 'too small to measure' on the case report form and has entered a smaller value that can be reliably measured. If a TL response of PD results, then this will be reviewed by the study team.

Irradiated lesions/lesion intervention

Previously irradiated lesions (i.e. lesion irradiated prior to entry into the study) should be recorded as NTLs and should not form part of the TL assessment.

Any TL (including lymph nodes), which has had intervention during the study (for example, irradiation / palliative surgery / embolisation), should be handled in the following way and once a lesion has had intervention then it should be treated as having intervention for the remainder of the study noting that an intervention will most likely shrink the size of tumours:

- Step 1: the diameters of the TLs (including the lesions that have had intervention) will be summed and the calculation will be performed in the usual manner. If the visit response is PD this will remain as a valid response category.
- Step 2: If there was no evidence of progression after step 1, treat the lesion diameter (for those lesions with intervention) as missing and if $\leq 1/3$ of the TLs have missing measurements then scale up as described in the 'Scaling' section below. If the scaling results in a visit response of PD then the patient would be assigned a TL response of PD.

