3.2.1.1.2 Best Objective Response [BoR] and Objective response rate [ORR]

BoR is calculated based on the overall visit responses from each RECIST assessment, described in Section 3.2.1.1.1. It is the best response a patient has had following first dose but prior to starting any subsequent cancer therapy and up to and including RECIST progression or the last evaluable assessment in the absence of RECIST progression. Categorisation of BoR will be based on RECIST using the following response categories: CR, PR, SD, PD and NE.

For the primary analysis of the primary endpoint CR or PR must be confirmed. Additional secondary analysis is planned to include assessment of unconfirmed responses for the primary endpoint (ORR by investigator assessment in accordance with RECIST 1.1) and secondary endpoint (ORR by BICR assessment in accordance with RECIST 1.1). A confirmed response of CR/PR means that a response is recorded at 1 visit and confirmed by repeat imaging not less than 4 weeks after the visit when the response was first observed with no evidence of progression between the initial and CR/PR confirmation visit. For determination of a best response of SD, the earliest of the dates contributing towards a particular overall visit assessment will be used. SD should be recorded at least 6 weeks minus 1 week (to allow for an early assessment within the assessment window), after first dose of study treatment. For CR/PR, the initial overall visit assessment which showed a response will use the latest of the dates contributing towards a particular overall visit assessment.

ORR is defined as the percentage of patients with a confirmed (or unconfirmed - depending on the analysis) investigator-assessed response of CR or PR and will be based on all treated patients (or a subset of all treated centrally confirmed FISH+, or all treated centrally confirmed by IHC).

Data obtained up until progression, or last evaluable assessment in the absence of progression, will be included in the assessment of ORR. Patients who discontinue study treatment without progression, receive a subsequent anti-cancer therapy (note that for this analysis radiotherapy is not considered a subsequent anti-cancer therapy) and then respond will not be included as responders in the ORR (i.e. the initial and confirmatory scan for a response must be prior to subsequent therapy for the patient to be considered as a responder).

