3.2.1.1.4 Change in tumour size

Change in tumour size at Week 12

Change from baseline in TL's tumour size at 12 weeks and over time will be based on RECIST TLs measurements taken at baseline and at post-baseline assessments. Tumour size is the sum of the longest diameters (or short axis measurements for lymph nodes) of the target lesions. Target lesions are measurable tumour lesions. Baseline for RECIST is defined to be the last evaluable assessment prior to starting treatment.

The percentage change in TL tumour size at post-baseline assessments will be obtained for each patient taking the difference between the sum of the TLs at timepoint and the sum of the TLs at baseline divided by the sum of the TLs at baseline times 100 (ie, $[\text{timepoint} - \text{baseline}]/\text{baseline} \times 100$). Only patients with measurable disease at baseline should be included in summaries of best percentage change in tumour size (measurable disease is as denoted on the CRF by the investigator).

No imputation will be used for summaries of the percentage change in tumour size from baseline by visit, but for summaries of the percentage change at Week 12, imputation will be used.

For patients who have less than or equal to one-third of TLs missing at week 12, assessment data from missing lesions may be scaled up proportionally to the sum of the corresponding lesions at baseline to give an estimated sum of diameters as described in the RECIST section of the protocol and Section 3.2.1.1.1 of this SAP. Whenever TL tumour size data for the visit is available then this should be used in the summary tables and figures.

If after applying these considerations there is still missing TL tumour size measurement data [tsm data] at week 12, the following imputation process for each individual patient where data is missing should be applied:

- a) If there is no observed TLtsm data at week 12, but there is TL tsm data collected at a visit prior to week 12 or the first visit after week 12, use all of the available data up to and including the first visit after week 12 (i.e. baseline and all visits up to and including the first visit after week 12) to fit a linear regression to the individual patient's baseline and follow-up assessment(s). Note that actual day of the measurement rather than planned day should be used in the fitting of this model. This model can then be used to generate an estimated value for TL tsm at week 12

and hence impute a change from baseline at week 12.

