- b) If there is no observed TL tsm data at week 12 but there is evidence of progression for the individual prior to the end of the time window used to select week 12 data, where evidence of progression is defined as progression of NTLs, the appearance of new lesions or as determined by an investigator (i.e. investigator's opinion of response recorded on the RECIST CRF is PD at that assessment or study treatment was discontinued for progression in the assessment time window), and there are at least 5 patients with non-missing TL tumour size who have also progressed then impute a change from baseline at week 12 as the median percentage change from patients with non-missing TL tumour size who also have progressed. If the patient has an imputed value from a), use the maximum of this median value or the imputed value in the tumour size analysis. However, if there are less than 5 patients with non-missing tumour size who have also progressed then impute a change from baseline at week 12 as 20%. If the patient has an imputed value from a), use the maximum of 20% or the imputed value in the tumour size analysis.
- c) If there is no evidence of progression for the individual, use the imputed value calculated in a) if data available. If there is no evidence of progression for the individual and no observed TL tsm data is collected at a visit prior to week 12 or the first visit after week 12, assume that the data is missing completely at random. The patient will be excluded from the analysis.
- d) If it is known that the patient has died prior to the end of the time window used to select week 12 data, impute a change from baseline at week 12 as the maximum of the observed or imputed (from step b) percentage change reported in the study for week 12.

Best percentage change in tumour size

The best percentage change in tumour size for each patient is the biggest decrease or the smallest increase in TL tumour size from baseline in the absence of a decrease.

If a patient has no post baseline assessments, then the following imputation rules should be applied:

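### Best percentage change in tumour size has no cut at subsequent anti-cancer therapy, so this exploratory summary and its waterfall can credit next-line shrinkage to study treatment

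*SAP*

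**What the plan says.** **Best percentage change.** SAP 3.2.1.1.4 defines it this way: "The best percentage change in tumour size for each patient is the biggest decrease or the smallest increase in TL tumour size from baseline". The tumour-size data behind it "will be based on RECIST TLs measurements taken at baseline and at post-baseline assessments". SAP 4.2.2.13.1 then summarises "the best percentage change in tumour size from baseline over all tumour assessment time points" and plots it as a waterfall for the TPAS. SAP 4.2.2.13.2 repeats this for the SAF dose groups. None of these sections mentions subsequent therapy or progression as an end point for the data; the imputation rules deal only with missing values.

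**Response.** SAP 3.2.1.1.2 does limit the data. Best objective response uses assessments "prior to starting any subsequent cancer therapy and up to and including RECIST progression". For ORR, "the initial and confirmatory scan for a response must be prior to subsequent therapy for the patient to be considered as a responder".

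**Scanning.** Under Protocol 7.1.3, patients who stop study drug before radiological progression are followed with tumour assessments "until RECIST 1.1-defined PD or death regardless of whether or not the patient started a subsequent anti-cancer therapy".

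**Status.** SAP Section 6 lists change in tumour size and best percentage change among the analyses added to those in the protocol, to be explored.

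**The concern.** Two summaries of the same target-lesion data stop at different points. Response stops counting when a new anti-cancer drug starts; best percentage change goes on until scanning ends. A patient who stops study drug for toxicity with little shrinkage, then responds to the next drug before RECIST progression, is a non-responder in ORR but a deep bar in the waterfall. That shrinkage would be displayed as an effect of savolitinib plus osimertinib.

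The waterfall is produced for the primary-endpoint population and will be read beside the ORR. What is at stake is how fairly that plot and its descriptive summary describe depth of shrinkage. No test or decision depends on them.

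**Working it through.** The plan states no figure on this point, so the check compares rules and follows their consequence.

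**1. Are post-switch scans collected?** Yes. Protocol 7.1.3 requires them until RECIST progression or death. Protocol 7.1.2 says patients who permanently stop study treatment should receive local standard of care, so new therapy before progression is foreseeable. SAP 4.2.2.3.1 plans a summary of response onset relative to subsequent therapy.

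**2. Does each endpoint exclude them?**

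| Endpoint | SAP section | Ends at new therapy? | Ends at progression? |
|---|---|---|---|
| Best objective response | 3.2.1.1.2 | Yes | Yes |
| ORR | 3.2.1.1.2 | Yes, for both initial and confirmatory scans | Yes |
| Best percentage change | 3.2.1.1.4, 4.2.2.13 | Not stated | Not stated |

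**3. Does another rule fill the gap?** No.
- Crossover (SAP 3.1.1): "their data will be cut off for the purposes of any savolitinib plus placebo assessment". This covers placebo-arm patients who move to the combination. SAP Table 3 lists tumour-size change only for the combination regimens.
- Lesion intervention (SAP 3.2.1.1.1): "once a lesion has had intervention then it should be treated as having intervention for the remainder of the study". The interventions named are local ones to a target lesion (irradiation, palliative surgery, embolisation), not a new systemic drug.
- SAP Section 6 adds the endpoint without restricting its data.

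**4. Direction.** Let A be a patient's percentage changes before the switch and B those after the switch and before progression.

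- As written: best change = min(A and B together) = min(min A, min B), which is never above min A.
- With the response data cut: best change = min A.

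The post-switch scans therefore leave the value unchanged (min B at or above min A) or make it more favourable (min B below min A). They cannot make it worse.

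**5. Illustration, with assumed values.** A patient is at -10% on study treatment, stops without progression, starts another drug and reaches -45% before progression.
- As written: min(-10, -45) = -45%.
- With the cut: -10%.
- Difference: 45 - 10 = 35 percentage points.

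The partial-response threshold in SAP Table 6 is a 30% decrease. The same patient would have a best objective response of stable disease, yet appear as a bar beyond -30%.

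**6. Where the argument stops.** It depends on taking a minimum. Week 12 change is a single value, observed or imputed, and a spider plot adds later points without altering earlier ones. Post-switch scans can contaminate both, but nothing fixes the direction.

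**7. Number affected.** Only patients who start a new drug before RECIST progression and are scanned afterwards can be affected, because scheduled scans end at progression. The share of bars that change cannot exceed the share of such patients. The documents do not give that share.

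**The case against.** The strongest case on the other side has four parts.

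- **The endpoint carries little weight.** It is exploratory, descriptive and added in the SAP, with no test or decision rule. This stands and sets the weight of the point. A reader might infer that the primary ORR is inflated too. It is not, because SAP 3.2.1.1.2 requires both scans of a response to precede new therapy.
- **A waterfall may differ from ORR for good reasons.** ORR needs confirmation, and new lesions or non-target progression override target-lesion shrinkage. This stands, so disagreement alone is no error. The defect is narrower: shrinkage under another drug is attributed to study treatment.
- **The size is unknown.** A reader might take the 31.8% savolitinib discontinuation for adverse events (Protocol Section 2) as a guide. It comes from an earlier phase I combination study at 600 mg od and counts stopping savolitinib only. Here such a patient may continue osimertinib, and SAP 3.2.2.4 counts therapy as subsequent only after the last dose of study treatment. An assumed switch rate of 5% to 15%, multiplied by the 30% chemotherapy reference ORR in SAP 4.2.2.1.1, gives 5% x 0.30 = 1.5% to 15% x 0.30 = 4.5% of bars. That ignores switchers already at -30% or better. If the 55% ORR assumed in Protocol 9.2 applied to them independently, the range becomes 1.5% x 0.45 = 0.7% to 4.5% x 0.45 = 2.0%. The reference ORR is also not measured from this trial's baseline. None of these figures is an estimate.
- **The one-way argument does not extend to every tumour-size output.** This stands: no directional bias is claimed for Week 12 change or spider plots. Cutting Week 12 data would also interact with the imputation steps in SAP 3.2.1.1.4.

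**Conclusion.** The point holds for best percentage change, in its summary and its waterfall, for both TPAS and SAF. Applied as written, the SAP includes scans taken under a later drug, and for a minimum these can act only in the favourable direction. No other section supplies the missing cut.

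The consequence is modest. The output is exploratory and the primary ORR is protected. The number of affected patients is not given and is probably small. The conclusion rests on two things: that at least some patients start a new systemic drug before RECIST progression, and that the SAP is programmed as it reads. The logical defect does not depend on any assumed rate. The missing cut at progression adds little, since only unscheduled scans after progression would be caught.

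**What to change.** In SAP 3.2.1.1.4 and 4.2.2.13, state that best percentage change (summary and waterfall, TPAS and SAF) uses only assessments made no later than RECIST progression and before any subsequent anti-cancer therapy, with the same cut-off date as best objective response. Use one definition of subsequent therapy throughout, including the ORR convention that radiotherapy does not count; local treatment of target lesions stays under the lesion-intervention rules.

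Patients left with no post-baseline scan should follow the existing best-change imputation and exclusion rules in SAP 3.2.1.1.4. Spider plots can be truncated or marked at the same date.

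Week 12 change is optional. If the cut is applied there, the SAP should say that excluded values are handled by steps (a) to (d) of the Week 12 imputation, and that the step (a) regression uses only scans before the switch.

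No new data are needed: SAP 3.2.1.1.6 shows that start dates of subsequent therapy are recorded, and the response cut must already be derived. For best change this is a short text and programming edit; Week 12 needs the extra wording above. The downside is that a few bars become less favourable, or are imputed or excluded.
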